3.2.2 Delay of Cell Infusion

Patients experiencing toxicities from their preceding treatments will have their Descartes-11 infusion schedule delayed until these toxicities have resolved to at least Grade 2 (excluding cytopenias), unless in the documented opinion of the medical monitor and treating physician it is reasonable to proceed. During this period, the patient will be assessed to record adverse events and a decision will be made on whether the patient meets criteria for cell infusion. Infusions can also be delayed up to 24 hours for scheduling reasons. Furthermore, prior to study cell infusion, subjects must have been free from fever, infection and organ dysfunction since qualifying for the study (See [Section 3.3.1.2](#) for details). If the patient does not meet infusion criteria, the infusion can be delayed up to 4 weeks.

3.3 Drug Administration

3.3.1 Preparation and Administration of Study Drug

3.3.1.1 Drug Preparation

3.3.1.2 Drug Administration

Prior to each infusion, patients must meet the following criteria:

1. Temperature is less than 37.9°C;
2. There are no signs of an active infection;
3. Last anti-myeloma agent was given at least 7 days prior
4. Other than a cytopenia, there are no ongoing Grade 2 toxicities from prior treatment precluding cell infusion unless PI documents that is reasonable to proceed, i.e. Grade 2 cough;
5. Pre-infusion clinical assessment does not suggest organ dysfunction and/or rapid disease progression since enrollment.

See [Section 3.2.2](#) for conditions to delay cell infusion and [Section 3.2.1](#) for dose definition. Administered dose must be within $\pm 45\%$ of defined dose. Final dose calculation will be based on actual manufactured cell numbers. Premedication for the cell infusion will be given within 15 to 120 minutes prior to the infusion. The medications are acetaminophen 500-1000 mg orally and diphenhydramine 25-50 mg intravenously or by mouth. **Prior to infusion, the cell product identity label must be double-checked by two authorized staff (MD or RN), and identification of the product and documentation of administration must be entered in the patient's chart as is done for blood banking protocols.** Please see detailed infusion instructions in the Descartes-11 Clinic Storage, Handling and Administration Manual.

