2.1 Eligibility Criteria

2.1.1 Inclusion Criteria

The following inclusion criteria will be applied at Screening, unless another evaluation time point is specified:

1. High-risk multiple myeloma patients (defined below) who complete pre-transplant induction treatment anti-myeloma drug combination (minimum 2 drugs).
2. Following completion of the pre-transplant induction regimen, patients must have residual disease measured by at least one of the following markers:
 - a. Serum M-protein detectable by immunofixation
 - b. Urine M-protein detectable by immunofixation
 - c. Abnormal FLC ratio
 - d. A biopsy-proven plasmacytoma or residual disease on imaging of a spot that was known to have plasmacytoma
 - e. Evidence of clonal cells in immunohistochemistry defined as Kappa/Lambda <4:1 or >1:2 after counting ≥ 100 plasma cells
 - f. Evidence of MRD detected by DNA-based or flow cytometry approaches
3. Patients must have high-risk multiple myeloma based on IMWG consensus as defined by R-ISS Stage III¹⁰ or high-risk CA³.
 - a. R-ISS Stage III is defined as having serum β -microglobulin ≥ 5.5 mg/L and either a high risk CA by iFISH or high LDH.
 - b. High-risk CAs are defined as having 1) t(4;14), t(14;16), t(14;20), or del(17/17p) in at least 20% of the cells; 2) any non-hyperdiploid karyotype, 3) gain(1q); 4) del 13; 5) gain 1q; or 6) a high-risk signature on gene expression profile (GEP).
4. There should be at least 7 days between the last dose of anti-myeloma drug and first Descartes-11 infusion.
5. Toxicities from prior therapies must have resolved to Grade 2 or less according to the CTCAE 5.0 criteria, or to the subject's pre-therapy baseline at the time of first cell infusion.
6. Patients must have signed written, informed consent.
7. Patients must be 18 years of age or older at the time of enrollment.
8. Patients must have clinical performance status of ECOG 0-2.
9. Patients must be seronegative for HIV.
10. Patients must be seronegative for hepatitis B (HBV) antigen; or, if the patient is positive for the hepatitis B antigen test, he or she must be negative for HBV DNA and must agree to use Hepatitis B prophylaxis as per institution guideline and/or principal investigator discretion.

11. Patients must be seronegative for hepatitis C (HCV) antibody; or, if the hepatitis C antibody test is positive, the patient must be tested for the presence of viremia by RT-PCR and must be HCV RNA negative.

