2.2.4 Early Withdrawal of Subjects

Patients who do not complete at least one Descartes-11 infusion will be considered to have prematurely discontinued the study. The reasons for premature discontinuation must be recorded on the case report form. Final study evaluations will be completed at the time of discontinuation. Provided that all protocol requirements are satisfied for the trial to continue safely, patients who withdraw early from the study will not be counted toward study recruitment limits.

[figure not shown]

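### Three passages set inconsistent conditions for releasing the first infusion when toxicity from prior therapy persists, and none says which prevails

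*Combined protocol and SAP*

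**What the plan says.** - **Section 2.1.1, inclusion criterion 5.** "Toxicities from prior therapies must have resolved to Grade 2 or less according to the CTCAE 5.0 criteria", or to the patient's "pre-therapy baseline at the time of first cell infusion". Inclusion criteria apply at screening unless another time is given; this one names the first infusion. It neither exempts cytopenias nor lets anyone waive it.
- **Section 3.2.2.** The infusion schedule is delayed "until these toxicities have resolved to at least Grade 2 (excluding cytopenias), unless in the documented opinion of the medical monitor and treating physician" going ahead is reasonable. There is no baseline alternative. A patient who does not meet the infusion criteria can be delayed by up to 4 weeks.
- **Section 3.3.1.2, item 4.** The list opens with "Prior to each infusion, patients must meet the following criteria". Item 4 begins "Other than a cytopenia, there are no ongoing Grade 2 toxicities" and in full requires that "there are no ongoing Grade 2 toxicities from prior treatment precluding cell infusion unless PI documents that is reasonable to proceed". Its example is a Grade 2 cough. It does not mention Grade 3.

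Sections 3.2.2 and 3.3.1.2 refer to each other. Neither refers to inclusion 5, and no text sets an order of precedence.

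**The concern.** All three passages bear on the same decision: whether a patient with unresolved toxicity may receive the first dose. They differ on the grade that matters, on whether return to baseline is enough, on whether cytopenias count, and on who may override the rule. The patients have just finished induction with at least two drugs, and the washout may be as short as 7 days, so residual toxicity is foreseeable.

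Two things are at stake. The first is patient safety: the same patient can be infused or held depending on the section consulted. Whether the medical monitor, who under Section 5.3 acts for the sponsor, must agree to an override also depends on the section. The second is conduct: a site can use an exemption or waiver that one section grants and, by doing so, breach another.

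**Working it through.** No figure in the plan is under test. Section 6 gives 34 patients, 10% against 35%, 80% power and a one-tailed 95% level. None of these uses residual toxicity as an input, so no recalculation applies. The check is to put the same patient through each rule.

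Other inputs:
- Inclusion 12: neutrophils above 1000 and platelets above 50,000 per mm³, at screening. No floor is given for other blood counts.
- Section 4.1.1: the screening window runs from Day -60 to Day 0.
- Section 4.1.2 and the study calendar: a blood count is taken before the Day 1 infusion.

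| Toxicity from prior therapy on Day 1 | Inclusion 5 | Section 3.2.2 | Section 3.3.1.2 item 4 |
|---|---|---|---|
| (a) Grade 3 cytopenia, worse than baseline | Not met; no waiver | Exempt | Exempt |
| (b) Grade 3 non-haematological, worse than baseline | Not met; no waiver | Delay; medical monitor and treating physician may waive | Not addressed |
| (c) Grade 3 non-haematological, equal to baseline | Met | Delay unless waived | Not addressed |
| (d) Grade 2 non-haematological, such as cough | Met | No delay | May need PI documentation |

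**Row (a)** is narrower than it first looks. Most patients with low neutrophils or platelets at screening are excluded by inclusion 12, and a cytopenia back at its pre-therapy grade passes inclusion 5. What remains is a cytopenia above Grade 2 and worse than baseline that either arose after screening or affects a count without a floor. The screening window and the missing floors leave room for this, and the Day 1 blood count can reveal it.

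**Row (b)** is a two-way conflict. Inclusion 5 offers no override; 3.2.2 offers one.

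**Row (c)** runs the other way: inclusion 5 is the more permissive rule because only it accepts return to baseline.

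**Row (d)** depends on how item 4 is read. Its wording reaches only Grade 2 toxicities that preclude infusion, so a Grade 2 toxicity judged harmless might fall outside it. But the item's own example for PI documentation is a cough, which the other two rules pass with no documentation.

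**The case against.** The strongest reply is that the rules are cumulative. Inclusion 5 sets eligibility, 3.3.1.2 lists what must hold before each infusion, and 3.2.2 says when to delay. All apply, and passing one never orders release. A tiered reading is also available: above Grade 2, delay unless the medical monitor and treating physician agree; at Grade 2, where the toxicity might preclude infusion, the PI documents the decision.

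Much of this stands for 3.2.2 against item 4, and for row (d) the practical consequence may be only a PI note. It does not rescue inclusion 5. If every condition must hold, inclusion 5 cancels the cytopenia exemption in both other passages and the waiver in 3.2.2 at the first infusion, where those provisions are expressly granted. Rows (a) and (b) therefore remain. In row (c), a site might argue that a condition back at its pre-therapy grade is no longer a toxicity of that therapy; 3.2.2 does not say so.

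Two stronger readings of item 4 should be resisted. A reader might infer that it flatly forbids infusion with any Grade 2 toxicity. The text does not support that, given its qualifier about precluding infusion and the PI's power to proceed. A reader might also infer that the PI alone can waive a Grade 3 toxicity. Item 4 names only Grade 2 and gives no such power; the only stated waiver above Grade 2 is in 3.2.2.

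**Conclusion.** The point holds as a safety and consistency fault in the treatment gate. Rows (a) and (b) are contradictions on the text, row (c) is one unless baseline-equivalent conditions are not counted as toxicities, and row (d) is an unclear extra requirement. This rests on reading the time stated in inclusion 5 as governing the whole criterion, which is its natural sense. The number of patients affected is unknown because the documents give no rate of residual toxicity.

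A reader might go further and infer that the conflict changes the primary denominator. Section 2.2.4 says that "patients who withdraw early from the study will not be counted toward study recruitment limits", and patients never infused are among them. One patient is 1/34 = 2.9 percentage points. In an exact one-sided test against 10%, 6/34 (17.6%) gives p = 0.119 and 7/34 (20.6%) gives p = 0.048. The documents do not support that step:
- Section 2.2.4 concerns recruitment limits, and Section 6 leaves the analysis to a separate SAP.
- A held patient is not a lost one, since up to 4 weeks of delay is allowed.
- If uninfused patients are replaced, the denominator stays at 34, and the rate moves only if the replacement responds differently. Nothing given links residual toxicity to response.
- The one-patient sensitivity would attach to any eligibility wording, and Section 6 does not name an exact test.

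Sample size, alpha and power do not change, and the effect on the responder rate cannot be computed.

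**What to change.** Reconcile the three passages into one rule, placed in Section 3.3.1.2, that states:
1. the grade allowed, covering Grade 2 and Grade 3 explicitly;
2. whether return to pre-therapy baseline is enough;
3. how cytopenias are handled on the day of infusion, and how this relates to the screening floors in inclusion 12;
4. who may waive the rule, at which grade, and how the waiver is documented;
5. whether the same rule applies to the first and to later infusions.

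Replace the wording in inclusion 5 and Section 3.2.2 with cross-references to it. The clinical team chooses the content of each item; this review takes no view on the threshold or on who should hold the waiver.

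The cost is protocol wording in three places. No procedures or visits are added, and the sample size is unaffected.

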3.3.2 Return or Destruction of Study Drug

The remaining thawed material should be discarded as per institution's biohazard waste removal procedures. Frozen Descartes-11 cells may require return to the Sponsor for a variety of reasons, including but not limited to: 1) condition of patient prohibits infusion/injection or 2) subject refuses infusion/injection or 3) extra product remains after completion of treatment. Sponsor will perform

ongoing reconciliation of drug shipped, drug consumed, and drug remaining. Drug destroyed on site will be documented in the study files.

3.3.3 Post-Infusion Observation

Emergency medical equipment (i.e., an emergency cart) must be available during the infusion in case the subject has an allergic response, or severe hypotensive crisis, or any other reaction to the infusion. Vital signs (temperature, respiration rate, pulse, blood pressure and oxygen saturation by pulse oximetry) will be measured prior to the infusion, within 10 minutes post infusion, then every 30 minutes (± 5 minutes) for two hours. If the vital signs are not satisfactory or not stable two hours post-infusion, vital signs will continue to be monitored at a minimum of every hour or as clinically indicated until stable. Following the 2-hour mandatory observation, the investigator will decide whether it is safe to discharge the patient. Patients will be required to monitor their temperature daily and report to the study team if it is $> 37.9^{\circ}\text{C}$. Follow-up assessments should include vital signs and a focused physical exam. At minimum, the following should be documented: ECOG performance status, cardiovascular exam, pulmonary exam and brief neurological exam. If clinically indicated, a more comprehensive evaluation should be added and documented in detail.

3.3.4 Management of Toxicities

For CAR T-cells, significant toxicities, if any, typically occur within one week of administration and include CRS and neurotoxicity. However, none of these have been observed in patients treated with Descartes-11 and recommendations below are based on published literature and common clinic practice.

The guidelines below are recommendations only and can be tailored to an individual patient's needs based on the judgment of the investigator or treating physician. Management that differs from these recommendations will not be considered a protocol deviation.

3.3.4.1 Febrile Reaction

Between Days 1 and 28 (or 14 days after first Descartes-11 infusion if cell infusion is delayed), fevers greater than 37.9°C will be assessed by the clinician and should be admitted for observation. To treat ordinary fever, a dose of ≥ 500 mg acetaminophen is recommended. Cooling blankets may be given if fever is greater than 40°C . In the unlikely event that the subject develops sepsis or systemic bacteremia following Descartes-11 cell infusion, appropriate cultures and medical management should be initiated. If a contaminated CAR T-cell product is suspected, the product can be retested for sterility using archived samples that are stored in the central manufacturing facility.

3.3.4.2 Infusion Reaction

Infusion-related reactions that occur during or within 24 hours following infusion were reported in less than 10% of patients participating in T-cell therapy trials, and most of the episodes were recorded as Grade 1 with a few reported as Grade 2.^{43,65}

The most recorded adverse event is nausea and taste disturbance (most likely due to the cryoprotectant, DMSO) and usually do not require any medical intervention. Oral ondansetron or prochlorperazine can be given for mild to moderate nausea. Additional doses of diphenhydramine and acetaminophen (if patient does not have > Grade 2 transaminitis) can be administered for mild to moderate infusion-related chills, itching, rash.

3.3.4.3 Allergic Reactions

Infusion-related allergic reactions should not occur frequently since Descartes-11 is an autologous cell product and its murine-derived sequences have been extensively humanized. Although highly unlikely, anaphylaxis has been reported in one patient who received mRNA-transfected anti-mesothelin CAR T-cell⁶⁶ and therefore an emergency cart should be present in the area where the patient receives the infusion. The clinical site's standard protocol for management of anaphylaxis should be followed.

3.3.4.4 Cytokine Release Syndrome

This protocol has adopted the CRS grading published by ASTCT for the grading system.⁴¹ See [Appendix A](#) for a recommended treatment algorithm, which will be used as a guidance and final treatment decision will be based on PI discretion. See [Section 4.3.1.2](#) for CRS-related blood collection procedures.

3.3.4.5 Neurotoxicity (ICANS)

Similar to CRS, this protocol has adopted the neurotoxicity grading published by ASTCT for the grading system.⁴¹ Management guidelines are summarized in [Appendix A](#). One of the earliest signs of developing neurotoxicity is aphasia, and should be monitored closely as these patients may require high-dose steroids for treatment of their neurotoxicity.

3.3.5 Concomitant Medications

3.3.5.1 Antibiotic Prophylaxis

It is recommended that patients with a CD4 T-cell count less than 200 will be maintained on pneumocystis prophylaxis as per institution guidelines. Other antimicrobial (antibacterial, antiviral or antifungal) prophylaxis is left to the discretion of the investigator. Antibiotics are typically indicated in neutropenic patients.

3.3.5.2 Blood Product Support

Using CBCs as a guide, the patient will receive platelets and packed red blood cells (PRBC's) as needed. Attempts will be made to keep Hb >7.0 gm/dL and platelets >10,000/mm³. Except for CAR T-cells, all blood products will be prepared and infused as per investigator's discretion.

3.3.5.3 Granulocyte Colony-Stimulating Factor

If the absolute neutrophil count becomes less than 1000/microliter and there is suspicion of or documented bacterial infection, then based on the investigator's discretion, growth factor support can be given. Growth factors should be discontinued once the ANC is above 1000/microliter.

3.3.5.4 Corticosteroids

Patients should not take systemic corticosteroids (including prednisone, dexamethasone or any other corticosteroid) that exceeds a dose equivalent to 40 mg/day or more of prednisone for any purpose without approval of the Principle Investigator. In addition, corticosteroids should be withheld for 12 hours before and 24 hour after the Descartes-11 infusion.

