8. TOCILIZUMAB SHOULD NOT BE GIVEN FOR ISOLATED NEUROTOXOCITY.
9. If the patient does not respond to tocilizumab within 12 hours, a repeat dose of tocilizumab can be given. If the patient does not respond to the second dose, corticosteroids (i.e. methylprednisolone 1mg/kg every 12 hours) should be prescribed.
10. Patients who are recovering from CRS should not be discharged until they are afebrile for at least 24 hours.
11. If neurotoxicity is suspected, the patient should be evaluated with the Immune Effector Cell Encephalopathy (ICE) scale⁴¹. Patients with Grade 2 neurotoxicity should get a neurology consult and thorough evaluation, e.g., with lumbar puncture and MRI, for other etiologies.
12. Patients who have Descartes-11 related neurotoxicity (except for headache) should receive dexamethasone in the following situations at 10mg/kg every 4-6 hours until symptoms regress to Grade 1:
 - a. grade 3 neurotoxicity lasting for 24 hours;
 - b. grade 4 neurotoxicity; or
 - c. any generalized seizure (in conjunction with other anti-seizure therapies).

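### The 24-hour post-infusion corticosteroid hold in Section 3.3.5.4 has no exception for the rescue dexamethasone called for in Appendix A, items 12b and 12c

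*Combined protocol and SAP*

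**What the plan says.** Section 3.3.5.4 has two sentences. The first says that patients should not take systemic corticosteroids at a dose "that exceeds a dose equivalent to 40 mg/day or more of prednisone for any purpose without approval of the Principle Investigator". The second adds a separate timing rule: "corticosteroids should be withheld for 12 hours before and 24 hour after the Descartes-11 infusion". Neither sentence mentions treatment of toxicity.

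Appendix A, item 12, says that patients with "Descartes-11 related neurotoxicity (except for headache) should receive dexamethasone in the following situations at 10mg/kg every 4-6 hours", continuing until symptoms fall to Grade 1. It lists three situations:

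- 12a: "grade 3 neurotoxicity lasting for 24 hours"
- 12b: "grade 4 neurotoxicity; or"
- 12c: "any generalized seizure (in conjunction with other anti-seizure therapies")

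Section 3.3.4.5 (neurotoxicity) refers management to Appendix A and foresees high-dose steroids. It does not mention the hold. Section 3.3.4 describes the toxicity guidance as recommendations that can be adapted to the patient, and adds: "Management that differs from these recommendations will not be considered a protocol deviation".

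**The concern.** The hold is written without a purpose or an exception, so on its face it covers steroids given as rescue. Items 12b and 12c describe emergencies for which the protocol itself wants dexamethasone, with no delay stated. A site that follows Section 3.3.5.4 to the letter would wait out the remainder of 24 hours before treating a Grade 4 neurotoxicity or a seizure. A site that follows Appendix A would give a drug that Section 3.3.5.4 says to withhold. No section states which instruction governs. What is at stake is the timing of rescue treatment in a rare but serious event, not the trial's inference.

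**Working it through.** The plan gives no figure to reproduce here. The check is a comparison of texts, plus arithmetic on the length of the hold.

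**Inputs.** Hold: 24 h after each infusion (Section 3.3.5.4). Infusions: Days 1, 4, 8, 11, 15 and 18 (Section 3.2.1). Dexamethasone interval: every 4 to 6 h (Appendix A, item 12).

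**Step 1: each trigger against the hold.** Let an event start *t* hours after an infusion, with *t* at least 0.

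| Item 12 trigger | Earliest time dexamethasone is called for | Clash with that infusion's hold (0 to 24 h)? |
|---|---|---|
| 12a, Grade 3 lasting 24 h | *t* + 24, so at least 24 h | No |
| 12b, Grade 4 | *t* | Yes, if *t* is below 24 h |
| 12c, generalized seizure | *t* | Yes, if *t* is below 24 h |

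The clash is therefore confined to two of the three triggers.

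**Step 2: how much time the hold covers.** Assume infusions run on schedule at the same clock time.

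- Shortest gap between infusions: 3 days = 72 h, so the 24 h windows do not overlap.
- Total post-infusion hold: 6 × 24 = 144 h.
- Span from the Day 1 infusion to 24 h after the Day 18 infusion: 17 × 24 + 24 = 432 h.
- Share of that span under the hold: 144 / 432 = 33%.
- Doses that a full 24 h hold would displace: 24 / 6 = 4 to 24 / 4 = 6.

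The 33% is a share of calendar time, not a probability that an event falls in the window.

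**Step 3: does any other text release the hold?**

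- The approval route in the first sentence of Section 3.3.5.4 attaches to the dose limit. The hold follows as an additional rule with no release route of its own.
- The waiver in Section 3.3.4 covers departures from the toxicity recommendations. A clinician who gives dexamethasone under item 12 is following those recommendations and departing from Section 3.3.5.4, which the waiver does not reach.
- Section 3.3.4.5 comes closest to settling the matter, since it names both Appendix A and high-dose steroids, but it does not rank them against the hold.

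**Step 4: how likely is overlap?** Section 3.3.4 places significant CAR T-cell toxicities, neurotoxicity among them, typically within a week of administration, but gives no share for the first 24 h. Section 1.2.5 says that CRS can begin on the day of infusion; that background concerns virally transduced cells, and no same-day statement is made for neurotoxicity. For Descartes-11 itself, Section 3.3.4 says of CRS and neurotoxicity that "none of these have been observed in patients treated with Descartes-11". No rate can be computed.

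**The case against.** The strongest reply is that the two texts do not really compete. Section 3.3.5.4 sits under concomitant medications, beside prophylaxis, transfusion and growth factors, while toxicity treatment has its own section and appendix. Wording about taking and withholding steroids most naturally describes background use around dosing, and a specific emergency instruction would ordinarily prevail over a general one. Both texts are advisory. Severe neurotoxicity is described in Section 1.2.6 as seen only with permanently modified cells, and Section 1.2.5 calls neurotoxicity less frequent in anti-BCMA trials.

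Most of this stands. It is why a clinician would probably treat, and why the point is minor. It does not remove the conflict. Section 3.3.5.4 does not limit itself to background use: its first sentence reaches use for any purpose, and the hold is added to that. The nearby Section 3.3.5.2 writes out its own exception, for CAR T-cells, so a stated exception would be in keeping with this part of the protocol.

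Two stronger readings are tempting, and the documents do not support them.

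- A reader might infer that the 40 mg/day approval sentence also obstructs rescue, because the item 12 dose is far above it. That sentence forbids nothing: it allows higher doses with approval and imposes no waiting time. Nothing in the documents shows that approval would delay treatment. The size of the item 12 dose relative to 40 mg/day says nothing about the 24-hour hold.
- A reader might infer that rescue dosing inside the window would have to be reported to the IRB or put through an exception form. Appendix A is part of the protocol, so following it is hard to call a change to the protocol under Section 5.2.5.2. Section 5.1.5 defines a deviation as unintentional, and Section 5.4 keeps formal reporting for deviations with material impact. Such consequences would be speculation.

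**Conclusion.** The point holds as a minor inconsistency in safety instructions. For a Descartes-11-related Grade 4 neurotoxicity or a generalized seizure within 24 h of any of the six infusions, Section 3.3.5.4 and Appendix A items 12b and 12c cannot both be followed, and nothing in the protocol says which prevails. Item 12a is not affected when onset follows the infusion. This rests on the wording alone. The frequency of the event is expected to be low and cannot be estimated, because the documents report no cases and give no onset times for neurotoxicity after Descartes-11. The endpoint, sample size and analysis are untouched.

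**What to change.** Add one sentence at the end of Section 3.3.5.4:

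*The 24-hour post-infusion hold does not apply to corticosteroids given to treat CRS, neurotoxicity or an allergic reaction under Section 3.3.4 and Appendix A.*

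CRS is included because Appendix A, item 9, calls for corticosteroids after two tocilizumab doses fail, which could fall inside the window if CRS starts early. Allergic reactions are included as a precaution: Section 3.3.4.3 defers to the site's anaphylaxis protocol, which is assumed here possibly to include a steroid.

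Leave the approval sentence unchanged. A blanket waiver of prior approval would go beyond the conflict shown. It would also remove a check on the item 12 dose, whose printed unit (mg/kg) deserves separate confirmation. The cost is one sentence of text.
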